694 Participants will be asked to record two days of baseline ketone values before initiating the use 695 of the study drug. Participant will then be directed to use the study CGM with Empagliflozin for 696 1-2 weeks. Proceeding to the pump treatment is dependent upon the participant's tolerance to 697 the medication. The study physician may elect to provide the participant additional time in the 698 event of medication side effects.

699 Participants will be instructed on the Glycemic Treatment Guidelines with special focus upon700 CGM readings (section 10.3) and Hyperglycemic Management (section 10.5).

- 701 Participant will meet the following criteria to continue study participation:
- 702 o Adherence to study protocol
- Ketone testing at least 2 times daily, preferably 4 times, with monitored values not
 greater than 0.6/mmol on at least two successive occasions (first measurement should be
 obtained upon waking in a fasting state)
- No adverse events relating to perineal infections, symptomatic postural hypotension, no
 evidence of significant hypoglycemia (< 54 mg/dl) or any other listed adverse effects of
 medication.

709 **9.2 Insulin Pump Training Visit**

Participants will receive pump training dependent upon the randomization group (i.e. Control-IQ
pump for 4 weeks then Basal-IQ pump for 2 weeks.) Training provided is described in Section
6.5.

713 **9.3 Optimization of Insulin Pump Settings**

- 714 Data driven optimization of pump settings can occur any time during the study, particularly if the
- study participant contacts the study physician due to concerns about their pump settings due to
- 716 recurring hypo- or hyperglycemia.

While initiating and maintaining Empagliflozin therapy, the study physician will carefully monitorinsulin dose reductions, especially basal insulin decreases.

719 9.4 Check-In Visits

All participants will be contacted by the study team in the week following the Run-In Phase and the Basal-IQ Pump Training Visits to address issues relating to the study equipment and side effect of the Empagliflozin if randomized to the treatment group. Two check-in visits will occur after the Control-IQ Training Visit. Extra contact with subjects will occur as needed.

724 9.5 Study Device Download

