1272 A DSMB will review all DKA and severe hypoglycemia irrespective of relatedness to study device 1273 use, and all serious events (including UADEs) related to study device use at the time of 1274 occurrence. The DSMB can request modifications to the study protocol or suspension or outright 1275 stoppage of the study if deemed necessary based on the totality of safety data available. Details 1276 regarding DSMB review will be documented in a separate DSMB document.

1277 Chapter 14 Miscellaneous Considerations

1278 **14.1** Prohibited Medications, Treatments, and Procedures

Participants using glulisine at the time of enrollment will be asked to contact their personal
physician to change their prescribed personal insulin to lispro or aspart for the duration of the
trial.

1282 The study devices (study insulin pump, study CGM) must be removed before Magnetic Resonance 1283 Imaging (MRI), Computed Tomography (CT) or diathermy treatment. Participants may continue 1284 in the trial after temporarily discontinuing use if requiring one of the treatments above.

1285 **14.2 Participant Withdrawal**

Participation in the study is voluntary. Participant may withdraw at any time. For participants
who do withdraw from the study, the study team will determine if their data will be used in
analysis.

1289 **14.3 Confidentiality**

For security and confidentiality purposes, subjects will be assigned an identifier that will be used instead of their name. Protected health information gathered for this study may be shared with the third party collaborators. De-identified subject information may also be provided to collaborators involved in the study after the appropriate research agreement has been executed.

1294 **Chapter 15 Statistical Consideration**

1295 **15.1 Design and Randomization**

1296 As presented in Figure 1, this study uses a randomized controlled design, with participants 1297 randomly assigned to four groups as follows:

- 1298a. Groups 1 and 2 are assigned to Experimental condition use of SGLT2 inhibitor1299(Empagliflozin) plus technology (CGM, Basal IQ or Control IQ)
- b. Groups 3 and 4 are assigned to Control condition no use of SGLT2 inhibitors;
 use of technology only (CGM, Basal IQ or Control IQ)

All four groups participate in a 1-2 week baseline CGM sessions, after which Groups 1 and 3 begin use of Control IQ, while Groups 2 and 4 begin use of Basal IQ. After using Control IQ or Basal IQ

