1304 for 4 or 2 weeks, respectively, all groups switch to use of the alternative technology (Figure 1).

The primary purpose of this pilot study is to evaluate the safety and efficacy of combining SGLT2 inhibitors with closed loop control, and to gauge the effect size of the outcomes listed below. Nevertheless, the projected sample size of N=40 (N= 60 recruited) participants is expected to

- 1308 results in statistically significant differences on some outcomes:
- 1309 Primary Outcome: CGM-measured time in the target range 70-180mg/dl (TIR) during the day;
- 1310 Hierarchical secondary outcomes: 24/7 CGM time in range <70mg/dl; 24/7 CGM-measured
- 1311 average glucose; CGM-measured glucose variability (coefficient of variation, CV) during the day;
- 1312 risks for hypo- and hyperglycemia.

1313 Analysis Overview: The overall analysis will follow Intention-to-treat (ITT) approach, with each 1314 participant analyzed according to the treatment assigned by initial randomization. The study 1315 design includes repeated measures on all outcomes; thus, we will use a linear mixed-effect model 1316 that corresponds well to this structure. The mixed model will use "Subject" as a random factor 1317 and "Group" as a fixed factor, e.g. using the Linear Mixed Models procedure in SPSS. We should 1318 note that similar results may be generated by repeated measures ANOVA, but mixed models 1319 handle missing data better (e.g. ANOVA only uses listwise deletion, which could reduce power 1320 and introduce bias towards study completers). A mixed model is also more flexible and will allow us to address additional questions, such as clustering of subjects or introducing time between 1321 1322 assessments as a continuous variable.

1323 Data Sources: Continuous glucose monitoring (CGM) data acquired every 5 minutes during the 1324 baseline and throughout the study. CGM data will be used to compute established metrics of 1325 glycemic control (e.g. time in ranges), risks for hypo- and hyperglycemia, e.g. the Low and High 1326 BG Indices (LBGI/HBGI), and CV, as recommended by the Consensus on Use of CGM, to which our 1327 team contributed substantially.

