- Handling of Missing Data: All randomized participants who have at least 50% of their CGM readings during the study period will be included in the analysis. Occasional missing CGM data do occur during normal CGM use and these values will be ignored when summary CGM metrics (e.g. percent times in range, LBGI, HBGI) are computed. Typically, CGM data are voluminous and the percent of missing values is low; thus no imputation would be required. For example, in the recently completed multi-center Protocol 3 of the International Diabetes Closed Loop Trial, N=168 subjects (of N=168 recruited) completed the entire 6-month protocol, and CGM data were
- 1335 available 96% of the time [15] (Table 1).
- 1336 Safety outcomes will be reported for all enrolled participants, irrespective of whether the 1337 subjects were randomized or the study was completed.
- 1338 Data Analysis: The objectives of this study are addressed by different sub-analyses of our general
 1339 analytical scheme, as follows:
- 1340Objective 1: Effect of adding Empagliflozin to predictive low glucose suspend (Basal IQ 21341weeks) and closed-loop control (Control IQ 4 weeks) will be assessed by the study1342randomized design (Figure 1). In this design we will have N=20 participants on Empagliflozin1343and N=20 participants off Empagliflozin, beginning with Control IQ and then switching to1344Basal IQ, or beginning with Basal IQ and then switching to Control IQ. This analysis will be1345done using the baseline data as covariates in a general linear model.
- 1346Objective 2: CGM-measured effect of Empagliflozin will be assessed using the baseline CGM1347data, (between Visits 2 and 3) via direct contrast between the two Experimental and two1348Control groups (N=20 participants in Groups 1-2 vs 20 participants in Groups 3-4);
- 1349Objective 3: CGM-measured effects of Empagliflozin added to Basal IQ will be assessed by1350direct comparison of the Experimental vs Control groups during the Basal IQ sessions (N=201351participants per arm will be available to this analysis);
- 1352Objective 4: CGM-measured effects of Empagliflozin added to Control IQ will be assessed1353by direct comparison of the Experimental vs Control groups during the Control IQ sessions1354(N=20 participants per arm will be available to this analysis);

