- 1355 To preserve the overall type 1 error, a hierarchical testing procedure will be used: if the primary 1356 analysis for CGM-measured TIR 70-180mg/dL during the day is statistically significant (p < 0.05), 1357 then testing will proceed to the next outcome metric in the following order: CGM-measured 24/7 1358 percent time <70mg/dL; CGM-measured average glucose; CGM-measured CV during the day; 1359 LBGI and HBGI. This process will continue iteratively moving to the next variable down on the list 1360 until a non-significant result ($p \ge 0.05$) is observed, or all variables have been tested. If a non-1361 significant result is encountered, then formal statistical hypothesis testing is terminated and any 1362 variables remaining on the list become exploratory.

1363 **15.2 Sample Size**

1364 Sample Size Determination is based on data from our Protocol 3 of the recently completed iDCL Trial (Table 1) conducted with the same algorithm in the same population. The Pre-Post changes 1365 in TIR in Table 1indicate effect size of >0.7 of Control IQ compared to SAP. Knowing the action of 1366 Basal IQ and Control IQ, and the action of Empagliflozin, we can assume that Empagliflozin will 1367 1368 double the effect of Basal IQ and Control IQ during the day and will preserve their benefits overnight. This, a 1:1 randomization into two Experimental vs. two Control groups and N=20 1369 participants per study arm, yields a sample size on N=40 subjects to complete the study. This 1370 1371 sample size was computed using the G*Power 3 software under the assumptions of power=90% 1372 and type 1 error α =0.01, further reinforcing the feasibility of the hierarchical analyses described above. In our experience with long-term AP studies, we observe attrition rate of 20%, with most 1373 dropouts occurring during the baseline prior to randomization. Thus, the recruitment sample size 1374 was increased to N=60 to accommodate up to 20% attrition rate without sacrificing statistical 1375 1376 power. We should also note that technology improvement appears to increase the retention rate 1377 in recent large-scale trials. For example, it the iDCL protocol 3, only 2 out of 170 recruited 1378 participants dropped out and all 168 randomized participants completed the 6-month study.

Table 1: Glycemic control	Baseline (2 weeks)		Post-Randomization (26 weeks)			
results from Protocol 3: N=168 patients who used Control IQ for 6 months	CLC	SAP	CLC	SAP	Differenc e	p value

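### Objective 1 adjusts for an undefined baseline; if that means the baseline CGM session, the covariate is measured after randomisation and on Empagliflozin, and the estimated drug effect shrinks

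*Combined protocol and SAP*

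**What the plan says.** - **15.1, Objective 1.** Twenty participants on Empagliflozin are compared with twenty off it, across Basal IQ and Control IQ. The analysis is done "using the baseline data as covariates in a general linear model". No variable, window or timing relative to first dose is given.
- **15.1, design.** "All four groups participate in a 1-2 week baseline CGM sessions, after which Groups 1 and 3 begin" Control IQ, while Groups 2 and 4 begin Basal IQ. The experimental condition for Groups 1 and 2 is the SGLT2 inhibitor ("Empagliflozin) plus technology (CGM, Basal IQ or Control IQ"), so the drug is paired with CGM as well as with each pump system.
- **9.1.1, run-in of the Empagliflozin group.** "Participant will then be directed to use the study CGM with Empagliflozin for" 1-2 weeks, before pump treatment starts.
- **15.1, Objective 2.** "CGM-measured effect of Empagliflozin will be assessed using the baseline" CGM data, contrasting Groups 1-2 with Groups 3-4.
- **Order of events (4.1, 5.2, 6.1, opening of Chapter 9).** Participants are randomised first to drug or no drug. Equipment training comes after randomisation, and the study CGM is handed out at that training.
- **Other uses of the word.** In 11.1.1 *baseline* refers to the screening HbA1c, and in 15.5 to demographic and clinical characteristics.
- **Purpose (15.1).** One stated purpose is "to gauge the effect size of the outcomes listed below".

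**The concern.** Adjusting a randomised comparison for a covariate is safe when the covariate is fixed before treatment can act on it. It then adds precision and leaves the treatment estimate unbiased. If the drug has already moved the covariate in one arm, the adjustment treats that movement as a pre-existing difference between the arms and subtracts part of it from the drug effect.

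Objective 1 does not say which kind of covariate it uses, and Chapter 15's own account of baseline CGM points to the unsafe kind. In a study meant to gauge effect size, the resulting estimate would be too small whenever the run-in effect and the later effect have the same sign. Two analysts following the same text could report materially different drug effects.

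**Working it through.** **Step 1. Is the baseline CGM session before or after randomisation?** By 4.1, 5.2, 6.1 and Chapter 9 the order is screening, randomisation, equipment training with issue of the CGM, then the session. It therefore follows randomisation. Figure 1 is not available in the text reviewed, and the readable visit schedule does not number visits, so Objective 2's reference to Visits 2 and 3 cannot be placed independently. The section texts nevertheless agree with one another on the order.

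**Step 2. Is it on drug in Groups 1-2?** Yes. Section 9.1.1 has them wear the CGM with Empagliflozin for the same 1-2 weeks, and Objective 2 reads a drug effect from those data. The same data cannot serve as a drug outcome in Objective 2 and as a drug-free covariate in Objective 1.

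**Step 3. Size of the bias if that CGM is the covariate.** The plan gives no figure on this point to reproduce. Let D be the true drug effect on the later outcome, f × D the drug effect already present in the run-in, and b the within-arm slope of later outcome on run-in value. The adjusted contrast is

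(difference in outcome) − b × (difference in covariate) = D − b × f × D = D × (1 − f × b),

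so the proportional loss is f × b. The slope b equals the correlation r times SD(later)/SD(run-in). The documents give neither f nor r. Table 1 in 15.2 does not settle the SD ratio either: its closed-loop arm gives 12/17 = 0.71 and its comparison arm 15/14 = 1.07. The values of b below are therefore assumed.

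| | b = 0.4 | b = 0.6 | b = 0.8 |
|---|---|---|---|
| Loss, f = 0 (covariate untouched by drug) | 0% | 0% | 0% |
| Loss, f = 0.5 | 20% | 30% | 40% |
| Loss, f = 1 | 40% | 60% | 80% |
| A true 10-point TIR gain, f = 0.5 | 8 | 7 | 6 |
| A true 10-point TIR gain, f = 1 | 6 | 4 | 2 |

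**Step 4. Check by simulation.** General linear model, 20 per arm, true gain 10 points, assumed SD 14 in both periods (so b = r), 4,000 runs. Mean estimates at r = 0.4 / 0.6 / 0.8:

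- f = 0: 9.88 / 10.03 / 10.01
- f = 0.5: 7.93 / 7.07 / 5.98
- f = 1: 5.95 / 4.05 / 2.06

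These agree with the formula.

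**Step 5. What it does to a test.** Take a true drug effect of 0.7 SD as an illustration (15.2 puts the Control IQ effect above 0.7 and assumes the drug doubles it). With 20 per arm and two-sided 0.05, power with no covariate is 58%. At r = 0.3 / 0.5 / 0.7, it is 60 / 70 / 85% with a covariate measured before the drug, and 31 / 21 / 13% with an on-drug covariate at f = 1.

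**The case against.** **The text does not force the harmful reading.** Objective 1 speaks of baseline data where Objective 2 specifies baseline CGM data, and 11.1.1 and 15.5 use *baseline* for screening measures. If those are meant, there is no such bias. This stands, and it makes the point conditional. It does not remove the ambiguity, because Chapter 15 describes no other baseline period for the CGM outcomes.

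**Drug effects without adjustment will be available anyway.** Objectives 3 and 4 are direct comparisons with no stated covariate, and the mixed model in the Analysis Overview names only Subject and Group. This also stands and limits the damage. A reader might infer that the primary result and the testing hierarchy are compromised. The documents do not support that: 15.1 does not say which objective carries the primary test, and 15.3.1, which concerns the drug added to closed-loop control, reads closer to Objective 4.

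**The percentages rest on assumptions.** True. They show how the loss behaves and are not a forecast. However, f = 0 is not a safe default: section 1.2 reports that the drug raised time in range in earlier trials, and Objective 2 exists to measure its effect in this very window.

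**A drug-free baseline might exist.** Section 9.1.1 says "Participants will be asked to record two days of baseline ketone values before initiating the use" of the drug, but these are ketone values, and the CGM-with-drug period comes after them. Section 15.2 mentions "dropouts occurring during the baseline prior to randomization", which a reader might take as proof that this trial's baseline precedes randomisation. That sentence reports the team's experience in earlier long-term studies and does not set the visit order here.

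**Conclusion.** The concern holds in conditional form. It is certain that Objective 1's covariate is undefined. It is also clear from the section texts that the baseline CGM session follows randomisation and is on drug in Groups 1-2. If that session supplies the covariate, the Objective 1 estimate is D × (1 − f × b), which is too small whenever the run-in and later effects share a sign. The illustrative loss is 20-40% at f = 0.5 and 40-80% at f = 1, for an assumed b of 0.4 to 0.8. If screening variables are used, the loss is zero.

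It would go too far to say that the plan commits to a biased analysis. Objectives 3 and 4 are unaffected, and a consequence for the testing hierarchy would arise only if Objective 1 were the primary analysis, which the plan does not state. The wording should be settled before the data are analysed. Confidence is medium, because the finding turns on which of two permitted readings the analyst takes.

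**What to change.** In 15.1, state that CGM recorded after the first Empagliflozin dose, together with the control groups' CGM from the same session, is an outcome for Objective 2 only and is not a covariate in any Empagliflozin contrast. For Objective 1, choose one of two options:

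- name a covariate already collected at screening, before randomisation, such as HbA1c; or
- use no covariate, in line with Objectives 3 and 4.

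The cost is two or three sentences, with no new data or visits. The downside is precision: HbA1c probably correlates less with later daytime time in range than a CGM covariate would, so its gain over no covariate may be small (58% against 60% power in the illustration at r = 0.3). Pilot participants who re-enter the Main Study have already had Empagliflozin, but a value taken before Main Study randomisation still leaves the comparison between arms unbiased.

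Optionally, add a clause in 15.2 saying that its remark about dropouts at baseline refers to earlier studies.

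### Section 15.1 claims overall type 1 error control but never says which Empagliflozin contrast opens the hierarchy; 15.3.1 favours Objective 4, while the Summary endpoint and 1.5 are worded as a device comparison

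*Combined protocol and SAP*

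**What the plan says.** Section 15.1 gives the trial's aim as "The primary purpose of this pilot study is to evaluate the safety and efficacy of combining SGLT2 inhibitors with closed loop control", and names the primary outcome as "CGM-measured time in the target range 70-180mg/dl (TIR) during the day". For the analysis in general, "we will use a linear mixed-effect model" with subject as a random factor and group as a fixed factor.

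The data analysis text then says "The objectives of this study are addressed by different sub-analyses of our general" scheme, and lists four contrasts of Empagliflozin against none, 20 participants per arm, without ranking them:

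- Objective 1: "Effect of adding Empagliflozin to predictive low glucose suspend" and to closed-loop control, that is, over both devices, "using the baseline data as covariates in a general linear model".
- Objective 2: "CGM-measured effect of Empagliflozin will be assessed using the baseline" CGM period.
- Objective 3: the drug effect during the Basal-IQ session.
- Objective 4: the drug effect during the Control-IQ session.

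The error-control paragraph follows: "To preserve the overall type 1 error, a hierarchical testing procedure will be used: if the primary" analysis of daytime TIR reaches p < 0.05, testing continues through a fixed list of outcome metrics and stops at the first non-significant one.

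**The concern.** A fixed sequence protects the error rate across the outcomes in the list for one contrast. It gives no protection across contrasts. The plan claims overall control but leaves the contrast in the first test unstated, so the choice between candidates could be made after the data are seen.

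The surrounding text adds to the doubt. Two prominent statements describe a comparison that does not estimate the drug effect, the comparator label in 15.3.1 is defined nowhere, and the daytime limit on the outcome comes and goes between sections. Objective 1 may also be adjusted for a covariate that the drug has already affected.

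**Working it through.** **Step 1. What each place implies about the primary analysis**

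| Place | Comparison implied | Daytime limit? |
|---|---|---|
| Summary, Objectives row | Drug combined with closed loop (fits Objective 4) | Not applicable |
| Summary, Endpoint row | Basal-IQ versus Control-IQ, on drug (none of the four) | No |
| 1.4 | Drug use in the Basal-IQ phase is exploratory | Not applicable |
| 1.5 | Control-IQ versus Basal-IQ, on drug (none of the four) | Not applicable |
| 1.8 | Outcome only | Yes |
| 15.1, purpose | Drug combined with closed loop (fits Objective 4) | Not applicable |
| 15.1, objectives | Four contrasts, unranked, Objective 1 first | Not stated |
| 15.1, hierarchy | A primary analysis, no contrast named | Yes |
| 15.2 | Two Experimental versus two Control groups, 20 per arm (fits all four) | Not applicable |
| 15.3.1 | Drug added to closed loop (fits Objective 4), comparator NO-AP-EMPA undefined | No |

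Objective 4 is the best-supported reading and Objective 1 is the main rival. No section gives clock hours for the day.

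**Step 2. Error rate if Objective 1 or Objective 4 may serve**

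Inputs from the plan: 20 versus 20 and level 0.05. Assumed: two-sided tests, equal session variances, the same unadjusted model for both, and a between-session correlation ρ from 0 to 0.9, because the documents give none.

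Let C and B be a participant's TIR in the Control-IQ and Basal-IQ sessions. Objective 4 tests C. Objective 1 tests an average of C and B. The correlation between the two test statistics is then:

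- equal weights: √((1+ρ)/2), which is 0.707 at ρ = 0, 0.866 at 0.5 and 0.975 at 0.9;
- 4:2-week weights: (2+ρ)/√(5+4ρ), which is 0.894, 0.945 and 0.989.

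Type 1 error = 1 − P(neither test rejects when there is no drug effect).

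| ρ | Equal weights, simulated (100,000 runs) | Equal weights, bivariate normal | 4:2 weights, bivariate normal |
|---|---|---|---|
| 0 | 8.4% | 8.3% | 7.1% |
| 0.3 | 7.8% | 7.8% | 6.8% |
| 0.5 | 7.4% | 7.3% | 6.5% |
| 0.7 | 6.8% | 6.8% | 6.2% |
| 0.8 | 6.5% | 6.5% | 6.0% |
| 0.9 | 6.1% | 6.0% | 5.7% |

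Simulation with 4:2 weights runs from 7.2% at ρ = 0 to 5.7% at 0.9. A repeat simulation gave 5.9% to 8.1% (equal weights) and 5.6% to 6.9% (4:2). A single named test simulates at 4.9% to 5.2%, which is the plan's nominal 5%.

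**Step 3. Model choice, kept separate**

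Fix the contrast at Objective 4 and leave only the choice between an unadjusted test and one adjusted for run-in TIR. The two statistics correlate at √(1−ρ²): 0.71 at ρ = 0.7, 0.60 at 0.8 and 0.44 at 0.9. The simulated chance that either rejects is about 8.1%, 8.7% and 9.2%. Unlike Step 2, it grows with ρ, because the two analyses drift apart.

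**Step 4. The baseline covariate**

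Under 9.1.1, Groups 1 and 2 use the study CGM on Empagliflozin for 1 to 2 weeks before the pump sessions. Objective 2 treats this same period as a measure of drug effect. If the baseline data in Objective 1 mean this CGM, the adjusted estimate is δ − b·δ₀, where δ is the drug effect in the session, δ₀ the effect in run-in and b the within-arm slope. With δ₀ = δ and equal variances (assumptions), b = ρ and the estimate becomes δ(1−ρ). Half the effect is removed at ρ = 0.5 and 90% at ρ = 0.9.

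**Step 5. Precision cost of choosing Objective 4**

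Standard error ratio, Objective 4 to Objective 1, equal weights, unadjusted: 1/√((1+ρ)/2) = 1.03 at ρ = 0.9 and 1.15 at ρ = 0.5.

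**The case against.** The strongest reply is that the contrast is all but named. Section 15.3.1 carries the primary efficacy heading and describes the drug added to closed loop. The Summary objective and the purpose in 15.1 agree, and 1.4 makes drug use with Basal-IQ exploratory. On this view only a cross-reference is missing, and in a pilot meant to gauge effect sizes the harm is small. Much of this stands, and it is why Objective 4 is the natural default. It does not close the point: Objective 1 is listed first, the sample-size text fits every objective, and the plan itself claims formal error control.

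Three stronger readings are tempting but not supported:

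- A reader might infer that the trial plans a device comparison as its primary test. Section 1.5 states a purpose and never calls it primary. The Summary applies that word only to the outcome variable. No device contrast appears among the four analyses. These are wording errors that need aligning.
- A reader might treat all four objectives as equal candidates and quote a much larger error rate. Objective 2 concerns the run-in, before any study pump session, and is not a plausible primary. Objective 3 is weakened by 1.4.
- A reader might take the 9% of Step 3 as the cost of the unnamed contrast. It comes from model choice. It also assumes that direct comparison, the phrase used for Objectives 2 to 4, may mean an unadjusted test. It could equally describe a contrast within the general mixed model.

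**Conclusion.** The concern holds in this form. The hierarchy in 15.1 controls error across outcomes for one contrast, and the contrast is not named, so the stated overall control is not secured. With Objectives 1 and 4 as the realistic candidates under a common unadjusted model, type 1 error is about 6% to 8% (equal weights) or about 5.6% to 7% (4:2-week weights), against 5%. At correlations of 0.7 to 0.9 the figures sit in the lower half of each range. An unfixed model is a separate problem that can take the error to about 9%.

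These sizes rest on assumed correlations, two-sided tests and equal variances. The textual findings rest on no assumption: the unnamed contrast, the device wording in the Summary endpoint and 1.5, the undefined comparator and the inconsistent daytime limit. The covariate problem is conditional on baseline data meaning the run-in CGM. Given the pilot status and the modest inflation, this should be fixed, but it does not invalidate the design.

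**What to change.** Before outcome data are analysed by arm:

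1. Name one contrast for the first test. The default is Objective 4, CiQ-EMPA versus CiQ-NO EMPA during the Control-IQ session, on TIR 70-180 mg/dL during the day, with the daytime window set by the sponsor.
2. Name one model for it, consistent with the mixed model in 15.1. Use only covariates recorded before the drug is started, for example screening HbA1c, and not run-in CGM.
3. Replace NO-AP-EMPA with CiQ-NO EMPA, and use the same statement of contrast and outcome in the Summary endpoint, 1.5, 15.1 and 15.3.1.
4. Apply the outcome hierarchy to that contrast only. Rank the other objectives after it, or label them exploratory and report 95% confidence intervals.

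The cost is wording and analysis only, with no change to participants, visits or sample size. The contrasts not chosen lose confirmatory status. If the drug effect is equal on both devices, Objective 4 has a standard error about 3% to 15% larger than Objective 1 at assumed correlations of 0.9 to 0.5, and the gap is wider if the correlation is lower.

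### Section 15.2's 90% power at alpha 0.01 with 20 per arm does not follow from its stated inputs: the drug-versus-no-drug contrast carries only the increment, about 0.7 SD at the plan's lower bound

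*Combined protocol and SAP*

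**What the plan says.** Section 15.2 builds the sample size in three steps.

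- From Table 1 (the earlier six-month Control-IQ trial) it takes an "effect size of >0.7 of Control IQ compared to SAP", where SAP means sensor-augmented pump.
- It assumes that Empagliflozin will "double the effect of Basal IQ and Control IQ during the day and will preserve their benefits" overnight.
- It concludes that 20 participants per arm, 40 completers in all, are needed. The "sample size was computed using the G*Power 3 software under the assumptions of power=90" per cent and a type 1 error of 0.01. It presents this as "further reinforcing the feasibility of the hierarchical analyses described above".

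Section 15.2 does not give the effect size entered, the SD, the G*Power test, the sidedness or any correlation.

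Section 15.1 sets the comparison. Groups 1 and 2 receive Empagliflozin plus the technology; Groups 3 and 4 receive the technology alone. Objective 1 covers the "Effect of adding Empagliflozin to predictive low glucose suspend" and to closed-loop control, with baseline data as covariates. Objective 4 is a "direct comparison of the Experimental vs Control groups during the Control IQ sessions", and Objective 3 does the same for Basal-IQ. For the repeated measures, "thus, we will use a linear mixed-effect model". The hierarchy moves past the primary outcome only if time in range "during the day is statistically significant (p < 0.05"). No Objective is named as the primary test.

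**The concern.** The printed effect describes a device against no automation. The trial randomises drug against no drug, with the device in both arms. If the drug doubles a device effect of 0.7 SD, the drug arm sits at 1.4 SD and the control arm at 0.7 SD, both measured against a reference that no arm of this trial receives. The randomised difference is the remaining 0.7 SD. A power of 90% at alpha 0.01 with 20 per arm looks too high for that difference.

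The figure is relied on. It is offered as support for a fixed-sequence procedure in which a primary p-value of 0.05 or more makes every later outcome exploratory. A reader who accepts 90% at 0.01 would think that outcome very unlikely at 0.05.

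**Working it through.** **Inputs.** 20 per arm, power 90%, alpha 0.01 and effect >0.7 (section 15.2); test level 0.05 (section 15.1); time in range in Table 1: Control-IQ 60 ± 17 before and 71 ± 12 after, sensor-augmented pump 59 ± 14 and 59 ± 15, difference +11 points. Sidedness is not stated; two-sided is used unless noted.

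**Increment in SD units.** The plan's lower bound is 0.7. From Table 1, the +11 difference gives 11/17 = 0.65, 11/15 = 0.73, 11/√((17² + 12²)/2) = 0.75, 11/√((12² + 15²)/2) = 0.81 and 11/12 = 0.917 (0.92 below).

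**The plan's own figure.** For a two-sample t-test, SE = √(2/20) = 0.316 SD, df = 38, and the noncentrality is d/SE. No stated input gives 20 per arm at 90%:

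- At d = 1.4 (twice 0.7), noncentrality is 1.4/0.316 = 4.43 and power at 0.01 is 95%; 17 per arm would suffice.
- At d = 0.7, noncentrality is 0.7/0.316 = 2.21 and power at 0.01 is 32% (42% one-sided); 90% would need 63 per arm.
- The effect giving 90% at 0.01 with 20 per arm is 1.28 SD (1.18 one-sided). Section 15.2 states neither value.

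**The randomised contrast under three analyses.** For the mean of two periods with between-period correlation r, the variance is multiplied by (1 + r)/2, which is 0.75 at r = 0.5 and 0.85 at r = 0.7, so SE = √(0.75 × 2/20) = 0.274 or √(0.85 × 2/20) = 0.292. With adjustment for a baseline that has the same correlation r with each period, the factor is (1 + r)/2 − r², which is 0.50 or 0.36 (df = 37). The correlations are assumptions; the documents give none. Averaging also assumes an equal increment on both devices, and Table 1 has no Basal-IQ effect.

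| Analysis, 20 per arm, two-sided | 0.7 SD: power at 0.01 / 0.05 | 0.92 SD: power at 0.01 / 0.05 |
|---|---|---|
| One device period, unadjusted | 32% / 58% | 58% / 81% |
| Both periods averaged, unadjusted, r 0.7 to 0.5 | 39-45% / 65-70% | 67-73% / 87-90% |
| Both periods, adjusted for a drug-free baseline, r 0.5 to 0.7 | 66-83% / 86-95% | 91-98% / 98% to over 99% |

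At 0.65 SD the first row is 27% / 52%.

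**Whether the third row is available.** It needs a covariate untouched by the drug. Section 9.1.1 has the Empagliflozin group record two days of ketone values and then use the CGM on drug for one to two weeks before the pump periods. Objective 2 uses the baseline CGM data themselves to contrast drug with no drug. As written, the drug arm's baseline is on drug, and adjusting for it could remove part of the effect under test. The third row therefore does not describe the plan as it stands.

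**The case against.** The strongest reply is that a two-sample t-test is not the planned analysis. Section 15.1 plans a repeated-measures mixed model, Objective 1 spans both devices with baseline covariates, and >0.7 is a lower bound. With 0.92 SD and a drug-free baseline, 90% at 0.01 is reached. It stands that 90% is not impossible under every set of assumptions. But section 15.2 states none of these assumptions, and the plan's own baseline is on drug for half the participants. Without that adjustment, 0.92 SD reaches at most 73%.

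The effect scale is also uncertain. Section 15.2 refers to changes from before to after, and Table 1 gives no SD of change. The raw gap after randomisation, 71 − 59 = 12 points, gives up to 12/12 = 1.0 SD, and one unadjusted period then has 67% power at 0.01. That is still short of 90%.

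The synopsis endpoint and section 1.5 can be read as a device comparison. A paired test in all 40 participants at 0.7 SD has 95% power at 0.01. It compares devices within person and does not test the drug.

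Section 15.1 also calls the trial a pilot meant to gauge effect sizes and expects significance on only some outcomes. That limits the consequence, but does not excuse a power figure used to support the testing hierarchy.

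A reader might infer that the doubled effect of 1.4 SD was entered in G*Power. The input is not printed, and 1.4 SD gives 17 per arm rather than 20, so the documents do not establish this.

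**Conclusion.** The point holds: 90% power at alpha 0.01 with 20 per arm does not follow from what section 15.2 states. On the plan's lower bound of 0.7 SD, the Empagliflozin-versus-none contrast has 32% power at 0.01 on one unadjusted period and 39-45% with both periods averaged. At the 0.05 used for testing these become 58% and 65-70%. At the top of the +11-point Table 1 range they are 58% and 67-73% at 0.01, and 81% and 87-90% at 0.05.

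The cancellation of the device effect follows from the design. The averaged figures rest on assumed correlations of 0.5 to 0.7 and an equal increment on both devices. A reader might go further and conclude that N=40 is wrong and that 63 per arm must be enrolled. The documents do not support that for a pilot whose primary test is not named. The defect is the stated power and the use made of it.

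**What to change.** Keep N=40. In section 15.2:

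- Name the Objective that is the primary test.
- Replace the 90% at 0.01 sentence with the power of that Empagliflozin-versus-none contrast at alpha 0.05, stating effect size, SD source, model, sidedness and any assumed correlation.
- Do not credit baseline adjustment in the power unless the covariate is CGM recorded before the first Empagliflozin dose. Reconcile Objective 1's baseline covariate with Objective 2 and section 9.1.1.
- Remove the statement that the size supports the hierarchical analyses unless the recomputed figure does so.

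Separately, the sample size rationale at the end of section 15.6 rests the doubling on urinary glucose loss at 10 mg, while section 5.2 gives 5 mg in the Main Study. These passages must be reconciled.

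The cost is rewording and one decision about the primary test. The stated power becomes less favourable. No patients are added, and neither treatment nor design changes.
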